8.4. AEs of Special Interest

For the AE of special interest (SIE) specified in the study protocol (as below), investigators need to fill in the "Adverse Event of Special Interest Report Form in Hengrui Clinical Study" within 24h after the event is known, and report to the sponsor. If it is SAE at the same time, please also fill in "Serious Adverse Event Report Form".

- \geq Grade 3 infusion reaction
- \geq Grade 3 immune related AE
- AEs that meet the criteria defined in Section 8.4.1 (Liver Function Test [LFT] Abnormalities)

8.4.1. Liver Function Test (LFT) Abnormalities

Considering the specialty of abnormal liver function at baseline in HCC subjects, abnormal values in ALT and/or AST concurrent with abnormal elevations of TBIL that meet the criteria outlined below (i.e., meeting the criteria [1] and [2] for elevated ALT or AST and bilirubin as well as the criterion [3]) in the absence of other causes of LFT abnormalities are considered important medical events and should always be reported as SIEs.

- 1) ALT or AST $\geq 3 \times$ ULN (normal at baseline), ALT or AST $\geq 3 \times$ baseline value (abnormally elevated at baseline)
- 2) TBIL $\geq 2 \times$ ULN (normal at baseline), TBIL $\geq 2 \times$ baseline value (abnormally elevated at baseline)
- 3) Excluding other causes of LFT abnormalities (e.g., disease progression, acute viral hepatitis, cholestasis, underlying hepatic disease, and concomitant medications with hepatotoxicity).

Subjects should return to the study center as soon as possible after learning the abnormal results (preferably within 48 hours). Evaluation should include laboratory examination, detailed medical history and physical evaluation.

Besides repeated measurement of AST and ALT, the laboratory examination should also include albumin, creatine kinase, total bilirubin, direct and indirect bilirubin, γ -glutamyl transferase, PT/INR, and alkaline phosphatase. Collection of detailed medical history should include history of alcohol, acetaminophen, soft drugs, various supplements, family history, occupational exposure, sexual behavior history, travel history, contact history with jaundice patients, surgery, blood transfusion, hepatopathy or allergic disease history. Further examinations also include detection of acute hepatitis A, B, C and E as well as radiological examination of liver (e.g., biliary passage).

8.5. Pregnancy

If the female subject is pregnant during the clinical trial, the subject must discontinue the study drug immediately; if the partner of male subject becomes pregnant during the clinical trial, the subject can continue the clinical trial.

For pregnancy of female subjects or partners of the male subjects during this study, investigators should fill in “Pregnancy Report/Follow-up Form in Hengrui Clinical Study”, and report to the sponsor within 24h after investigator awareness, and report to the ethics committee in time.

The investigator should follow up the pregnancy result, until one month after delivery, and will report the result to Sponsor and Ethics Committee.

If the outcome of pregnancy is stillbirth, spontaneous abortion, or fetal malformations, it should be considered as an SAE and be reported in accordance with SAE reporting requirements.

If an SAE occurs during pregnancy, the investigator is required to complete the “Serious Adverse Event Report Form” and report this SAE according to the reporting procedures.

9. CLINICAL MONITORING

In order to make sure the subject’s rights are protected, all the data should be reported accurately, completely and reliably. The trial should be conducted in accordance with currently approved protocol/revised protocol, ICH GCP and appropriate regulations; clinical monitoring is needed for the study center.

10. STATISTICAL ANALYSIS

A statistical analysis plan (SAP) will be prepared to provide further details regarding the definition of analysis variables and analysis methodology to address all study objectives. The SAP will serve as a compliment to the protocol and where there is a discrepancy between the SAP and protocol, the SAP will supersede it. Any critical revision within the SAP of definition(s) or analysis method(s) for the primary endpoints will be included in a protocol amendment.

10.1. Sample Size Determination

According to our previous phase II trial of single agent of apatinib on advanced osteosarcoma, the 4-m PFS rate was 56.76% (95% CI 39.43%–70.84%) and the 6-m PFS rate was 36.77% (95% CI 21.48%–52.16%). 9/37 (24.32%) patients was progression free at 6 months. Median PFS and OS were 4.44 (95% CI 3.12–7.08) and 8.77 (95% CI 6.73–16.70) months, respectively. This trial was designed to discard a PFS at 6 month of 37% (null hypothesis) aiming to reach a PFS at 6 month of 60% or higher (alternative hypothesis). Using Simon’s optimum two-stage design and setting α -error at 0.05 and β -error at 0.10, the presence of at least six successes in the 12 patients enrolled in the first stage allowed the trial to proceed to the second stage in which 31 more patients were needed to be enrolled for the minimum total of 43 patients. Power and sample calculations were performed using EAST® 6.4.1. software package.

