| Study Design | 
This is a Single-arm, Open label, Prospective, Single-center Clinical Trial to evaluate the efficacy and safety of PD-1 antibody SHR-1210 plus Apatinib Mesylate Tablets in patients with advanced Osteosarcoma.
 
Primary efficacy endpoint is 6 months PFR based on RECIST v1.1, and approximately 38 subjects who could be evaluated will be enrolled.
 
Subjects will receive study treatment after being informed of all pertinent aspects of the study, signing the informed consent form and passing the screening for eligibility. SHR-1210, 200 mg, via intravenous infusion, once every two weeks (Q2W) + Apatinib Mesylate Tablets 500 mg, p.o., once per day (QD), continuously, 4 weeks (28 days) per cycle of therapy, until meeting the criteria for study treatment termination specified in the protocol. Subjects will continue to receive safety and survival follow-up after end of treatment. Subjects who discontinue treatment for reasons other than progression of disease will continue to receive regular radiological evaluation follow-up after end of treatment.
 
Subjects will have safety visits on D1 of every 2 cycles; Radiological examination will be performed once every 8 weeks to evaluate efficacy until progression of disease is determined (non-pseudoprogression), start of a new anti-tumor therapy, withdrawal of informed consent, death, or termination of the study by the sponsor, whichever comes first.
 |
| Study Drug | 
SHR-1210 for Injection (Generic Name: Camrelizumab for Injection) (Manufacturer: Suzhou Suncadia Biopharmaceuticals Co., Ltd.)
 
Apatinib Mesylate Tablets (Manufacturer: Jiangsu Hengrui Medicine Co., Ltd.)
 |
| Route of Administration | 
SHR-1210 200 mg will be infused intravenously (premedication is not required). Each infusion will be administered over 30 min (no less than 20 min, no more than 60 min), once every two weeks;
 
Apatinib Mesylate Tablets 500 mg is administered orally after meals within 30 min, once per day, continuously.
 |
| Inclusion Criteria | 
Subjects can be enrolled in this study only when they meet all the inclusion criteria:
 
 1. Provided informed consent and sign the informed consent form; 2. ≥ 11 years old, male and female; |

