| 
Evaluation
 | 
have their survival status collected through site visits or telephone follow-up on a regular basis until death. Subject who died during the trial, their actual time of death will be recorded.
 
6 months PFR: defined as the progression free survival rate at 6 months after enrollment. Evaluations of PFR well as PFS, ORR, DCR and DoR will be performed based on RECIST v1.1 and iRECIST: The radiological evaluation will be performed once every 8 weeks; and can be performed in a real-time manner if new lesion is suspected; the efficacy must be confirmed in 4 weeks for the subjects who are firstly evaluated as PR/CR. The progression of disease that is suspected as pseudoprogression needs to be confirmed in subsequent radiological examinations, the time of the radiological examination for confirmation is at least 4 weeks after progression of disease is found or at the next scheduled time point (not exceeding 12 weeks), and prior to termination of study treatment. The patients who meet RECIST v1.1 criteria for progression will continue to receive tumor assessment until progression of disease (meeting the definition of iRECIST) or termination of study treatment, whichever occurs later. Once clinical progression occurs at any time, physical examination and immediate confirmation by imaging rather than waiting for the next scheduled imaging examination need to be done for the subject.
 |
| 
Sample Size Determination
 | 
The trial was designed to discard a PFS at 6 month of 37% (null hypothesis) aiming to reach a PFS at 6 month of 60% or higher (alternative hypothesis). Using Simon's optimum two-stage design and setting α-error at 0.05 and β-error at 0.10, the presence of at least six successes in the 12 patients enrolled in the first stage allowed the trial to proceed to the second stage in which 31 more patients were needed to be enrolled for the minimum total of 43 patients.
 |

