3. STUDY DESIGN

3.1. Overall Design

This is a Single-arm, Open label, Prospective, Single-center phase II trial to evaluate the efficacy and safety of PD-1 antibody SHR-1210 plus apatinib mesylate as seconde/third-line therapy in patients with advanced osteosarcoma.

The study will be conducted in subjects with incurable, locally advanced or metastatic osteosarcoma who had progressed upon first-line/second-line chemotherapy including high-dose methotrexate, doxorubicin, cisplatin with or without ifosfamide. Primary efficacy endpoints include both CBR and PFS evaluated by the BIRC based on RECIST v1.1, and approximately 43 subjects will be enrolled. Eligible subjects will receive SHR-1210 combined with apatinib mesylate (experimental arm).

Subjects will receive study treatment after being informed of all pertinent aspects of the study, signing the informed consent form and passing the screening for eligibility. Experimental arm: SHR-1210, 200 mg, via intravenous infusion, once every two weeks (Q2W) + apatinib mesylate 500 mg, p.o., once per day (QD), continuously, 4 weeks (28 days) per cycle of therapy, until meeting the criteria for study treatment termination specified in the protocol. Subjects will continue to receive safety and survival follow-up after end of treatment. Subjects who discontinue treatment for reasons other than progression of disease will continue to receive regular radiological evaluation follow-up after end of treatment.

The subject will continue to receive study treatment until intolerable toxicity occurs, or until lack of clinical benefits as determined by investigator after comprehensive evaluation of radiological and laboratory examination data as well as the subject's

clinical condition (e.g., tumor symptomatic exacerbation), or until the subject voluntarily withdraws from study treatment, whichever comes first.

Following disease progression in accordance with RECIST v1.1 (evaluated by investigator), subjects may continue treatment with SHR-1210 monotherapy or in combination with apatinib, if they can still clinically benefit from and tolerate study treatment as determined by investigator (see Section 6.6 for treatment criteria after disease progression).

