10.2. Objectives and Statistical Hypotheses

10.2.1. Primary Objectives and Statistical Hypotheses

Objectives: To compare efficacy endpoints of CBR and PFS evaluated by the BIRC based on RECIST v1.1 in one experimental arm (SHR-1210 in combination with apatinib).

Null Hypothesis: SHR-1210 in combination with apatinib PFS at 6 month of 37%.

Alternative Hypothesis: SHR-1210 in combination with apatinib PFS at 6 month of 60% or higher.

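### With a go rule of at least 6 of 12, the two-stage design cannot have 90% power at 60%; its exact power is at most 82% with alpha held at 0.05

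*Protocol*

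**What the plan says.** Section 10.1 sets the null 6-month progression-free rate at 37% and the alternative at 60% or more. It names Simon's optimum two-stage design with alpha 0.05 and then gives the type II error and the first-stage rule together: "error at 0.10, the presence of at least six successes in the 12 patients enrolled in the first stage". The second stage follows: "31 more patients were needed to be enrolled for the minimum total of 43 patients". The synopsis (Sample Size Determination) and section 10.4.5 repeat the same gate, error rates and total. Section 10.2.1 restates the alternative as "SHR-1210 in combination with apatinib PFS at 6 month of 60% or higher".

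Two sample sizes appear. The synopsis, under Study Design, says "approximately 38 subjects who could be evaluated will be enrolled", while section 3.1 says "approximately 43 subjects will be enrolled". No dropout rate is given to connect them, and no final success cut-off is stated for either total.

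**The concern.** In a two-stage design with a futility stop, a trial that fails the first stage cannot be recovered later. The probability of passing that stage under the alternative is therefore a ceiling on power. Six of 12 is a demanding threshold when the expected number at 60% is only 12 × 0.60 = 7.2, and it looked too strict to be compatible with a type II error of 0.10.

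The statement is the only sample-size justification for the primary endpoint. If it is wrong, a negative result would be read against 90% power that the design never had, and the risk of abandoning an active regimen after 12 patients is understated. With both 38 and 43 in the text, the reader also cannot tell which total the error rates describe.

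**Working it through.** **Inputs.** p0 = 0.37, p1 = 0.60, alpha 0.05, beta 0.10, go if X1 ≥ 6 with n1 = 12, n2 = 31, N = 43 (section 10.1); 38 evaluable (synopsis, Study Design). Alpha is taken as one-sided, as is usual for a Simon design; the protocol does not say.

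**Step 1: the gate.** With X1 ~ Bin(12, 0.60), the probabilities of 5, 4, 3 and 2 successes are 0.1009, 0.0420, 0.0125 and 0.0025; 0 and 1 together add 0.0003. So

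P(X1 ≤ 5 | 0.60) = 0.158 and P(X1 ≥ 6 | 0.60) = 0.842.

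The first stage alone loses 0.158, more than the stated beta of 0.10. No final cut-off and no second-stage size can lift power above 0.842. Under the null, P(X1 ≤ 5 | 0.37) = 0.741.

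**Step 2: the stated figure, with the best final cut-off.** For a final rule of at least r successes in N,

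P(success | p) = Σ over x from 6 to 12 of P(X1 = x) × P(Bin(N − 12, p) ≥ r − x).

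| N | Success if | Alpha at 37% | Power at 60% |
|---|---|---|---|
| 43 | ≥ 20 | 0.0779 | 0.832 |
| 43 | ≥ 21 | 0.0499 | 0.819 |
| 43 | ≥ 22 | 0.0292 | 0.795 |
| 38 | ≥ 18 | 0.0791 | 0.826 |
| 38 | ≥ 19 | 0.0489 | 0.805 |

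The stated 90% is not reproduced. With alpha at or below 0.05 the most that 43 patients give is 0.819, and 38 give 0.805.

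**Step 3: which design the gate belongs to.** An exhaustive search for the smallest expected sample size under the null, with alpha ≤ 0.05, gives:

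| Beta | Go if | Success if | Alpha | Power | Expected null size |
|---|---|---|---|---|---|
| 0.20 | ≥ 6 of 12 | ≥ 19 of 38 | 0.0489 | 0.805 | 18.7 |
| 0.10 | ≥ 9 of 20 | ≥ 22 of 44 | 0.0462 | 0.901 | 27.2 |

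The first row matches both the gate and the synopsis figure of 38. The second needs 20 patients at the first stage, not 12. The same two designs are optimal if p0 is the unrounded 36.77% in section 10.1. With the stated gate and 43 patients, the expected null size is 12 + 31 × (1 − 0.741) = 20.0, above 18.7, so that combination is not the optimum for beta 0.20 either.

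**Step 4: variations.** A looser gate of at least 5 of 12 with 43 patients gives power 0.873 at alpha 0.036 (≥ 22), or 0.907 only at alpha 0.065 (≥ 21). A single-stage rule of ≥ 22 of 43 gives alpha 0.040 and power 0.909, but that is not the stated design. Null rates of 35%, 36%, 38% and 40% and other error rates did not produce 6 of 12 with 43 as an optimum at 90% power.

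**Step 5: where 90% is reached.** With the stated gate, power first reaches 0.90 at a true rate of 64.2% (≥ 21 of 43) or 64.6% (≥ 19 of 38). The gate alone is passed with probability 0.90 only from 63.8%.

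**The case against.** The arithmetic of the gate is not open to dispute, and no later analysis plan could make this gate reach 90% at 60%. Four points can be made on scope.

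- **The 82% depends on the final cut-off.** The protocol gives none, and the unconditional ceiling is 84.2%. This is correct, but getting above 0.819 with 43 patients means exceeding the stated alpha, as the ≥ 20 row shows.
- **The alternative covers rates above 60%.** Power is quoted at the design rate, though, and 90% needs about 64%.
- **38 and 43 may be evaluable and enrolled numbers.** This is a reasonable reading; a 10% allowance would give 38/0.90 = 42.2, rounded up to 43. It remains an assumption, because no dropout rate is stated, section 10.1 presents 12 + 31 = 43 as the Simon total, and the synopsis says that the 38 are to be enrolled. If 38 is the analysed number, power is lower still.
- **The error concerns power, not false positives.** This stands. With ≥ 21 of 43 or ≥ 19 of 38, alpha stays below 0.05. Given that the gate is passed, power at 60% is 0.819/0.842 = 0.973 or 0.805/0.842 = 0.956. The loss sits almost entirely at the first stage.

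The documents also do not prove which entry is the slip. That beta was meant to be 0.20 is an inference from the match with 6 of 12 and 38.

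**Conclusion.** The stated design property is wrong. At a true rate of exactly 60%, a gate of 6 of 12 caps power at 84.2%. With alpha held at 0.05, power is 0.819 if 43 are analysed and 0.805 if 38 are. The chance of missing a true 60% rate is therefore at least 18.1% (43) or 19.5% (38), against the stated 10%, and 15.8 percentage points of it arise after 12 patients. The figures assume exact binomial counting of successes, every patient evaluable, and one-sided alpha of 0.05. The mismatch between 38 and 43 is secondary, but it has to be settled before any error rate can be attached to a total.

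**What to change.** Restate beta as about 0.20, that is, power of about 80% to 82% at 60%, and say which total is the analysed one:

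- **38 analysed (12 + 26):** success at ≥ 19, alpha 0.0489, power 0.805. Describe 43 as an enrolment allowance and state the assumed dropout rate.
- **43 analysed (12 + 31):** success at ≥ 21, alpha 0.0499, power 0.819. Drop the word optimum, since 6 of 12 with 43 is not the Simon optimum for either beta.

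Use the same numbers in both synopsis entries and in sections 3.1, 10.1 and 10.4.5. The cost is wording only: gate and enrolment stay as they are, and the stated power becomes less favourable.

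If 90% power at 60% is really required, the design itself must change; the optimum is then ≥ 9 of 20 followed by ≥ 22 of 44, with a larger first stage and an expected null size of 27.2 instead of 18.7.

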1.2.2.3.2 Exploration of Combination Administration in Preliminary Clinical Studies

Since October 2016, Jiangsu Hengrui Medicine Co., Ltd. has served as a funder or sponsor to conduct a number of clinical trials of SHR-1210 combined with apatinib mesylate, involving a variety of solid tumors such as advanced hepatocellular carcinoma, advanced lung cancer, advanced intrahepatic cholangiocarcinoma, advanced gastric adenocarcinoma and advanced triple-negative breast cancer. These studies explored the safety and tolerance of SHR-1210 combined with apatinib mesylate and the initial efficacy against a variety of tumors.

Preliminary results confirm: for SHR-1210 200mg fixed dose, once every two weeks (Q2W) combined with apatinib mesylate 250 mg/d, continuous oral dose level is tolerable, while the combination regimen for a variety of tumors have shown a significant efficacy, significantly increasing the proportion of subjects benefiting from treatment.

| Study Title | Study Design | First case enrolled/case number | Registration Number of Clinical Trial |
|--|--|---------------------------------|---------------------------------------|
| Exploratory clinical study of PD-1 antibody SHR-1210 combined with apatinib mesylate in the treatment of advanced gastric cancer and hepatocellular carcinoma | Dose-finding, dose expansion, phase Ib study | 2016-10/48 | NCT02942329 |
| Phase II clinical study of PD-1 antibody SHR-1210 combined with apatinib mesylate in the treatment of advanced non-small cell lung cancer | Dose-finding, dose expansion, phase II study | 2017-3/99 | NCT03083041 |
| Phase II clinical study of PD-1 antibody SHR-1210 combined with apatinib mesylate or chemotherapy in advanced primary liver cancer or extrahepatic cholangiocarcinoma | Dose-finding, dose expansion, phase II study | 2017-4/96 | NCT03092895 |
| One-arm, open-label, prospective, multicenter clinical study of the efficacy and safety of apatinib mesylate in combination with PD-1 antibody (SHR-1210) in the treatment of progressive osteosarcoma with chemotherapy failure | One-arm, open-label, phase II study | 2017-12/37 | NCT03359018 |
| Two-arm, open-label, investigator-initiated phase II clinical trial of anti-PD-1 antibody SHR-1210 in combination with apatinib mesylate in the treatment of recurrent metastatic triple-negative breast cancer | Two-arm, open-label, phase II study | 2017-12/23 | NCT03394287 |

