| One-arm, open-label, phase II clinical trial of anti-PD-1 antibody SHR-1210 combined with apatinib mesylate in the treatment of advanced hepatocellular carcinoma | One-arm, open, phase II study | 2018-3/122 | NCT03463876 |
| Phase II clinical study of SHR-1210 combined with apatinib mesylate in the treatment of extensive-stage small cell lung cancer with first-line standard of care failure | phase II study | 2018-1/1 | NCT03359018 |

Cut-off date: 25 Aug 2018

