16. PROGRESSION IN CLINICAL STUDY

Estimated enrollment for first subject in: Jan 2018

Estimated enrollment for last subject in: Jan 2019

Estimated end of study: Jun 2019

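### The 12-patient gate needs 6-month outcomes, but the protocol states no accrual hold, names no stage-1 review, and gives an enrolment calendar with little room for a pause

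*Protocol*

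**What the plan says.** Section 10.1 tests a null 6-month PFS rate of 37% against an alternative of 60% or more, with alpha 0.05 and beta 0.10 under a Simon optimum two-stage design. The gate is that "at least six successes in the 12 patients enrolled in the first stage allowed the trial to proceed to the second stage". Stage 2 then adds 31 patients to the first 12, for 43 in all. The Synopsis and Section 10.4.5 repeat this, and Section 3.1 agrees on the total: "approximately 43 subjects will be enrolled".

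The Synopsis (Efficacy Evaluation) defines the 6-month rate from enrolment. The Synopsis (Study Period) and Section 16 estimate the first subject in January 2018, the end of study in June 2019, and "Estimated enrollment for last subject in: Jan 2019". Section 4.6 instead places the last visit about 18 months after the last enrolment.

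Section 10.5 ties the Data Monitoring Committee's (DMC) efficacy analyses to the PFS analysis and the OS interim. Section 4.5 gives only general reasons for interrupting or ending the study. Nowhere does the protocol say whether enrolment pauses after patient 12, when or by whom the gate is read, or how patients enrolled in the meantime are counted.

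**The concern.** A two-stage design earns its small first stage by committing few patients before an inactive regimen can be dropped. That works only if stage-2 enrolment waits for the stage-1 result. Here the outcome takes 6 months to observe, which is about half of the whole planned enrolment window. If sites keep enrolling through the wait, a stop arrives after many of the patients it was meant to spare have started treatment, and the expected sample size under the null is no longer the one the design implies. Enrolment dates, DMC triggers and accrual holds govern trial conduct. The protocol already fixes the first two, so the third cannot simply be left to an analysis plan.

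**Working it through.** **Inputs.** From Sections 10.1 and 16 and the Synopsis: null 0.37, alternative 0.60, n1 = 12, go if at least 6 successes, total 43, outcome at 6 months, window January 2018 to January 2019 (12 to 13 months). No accrual rate is stated, so uniform accrual over the window is an assumption.

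**1. The stated design.**
- P(stop | 37%) = P(X ≤ 5 | 12, 0.37) = 0.741.
- Expected sample size at the null = 12 + 31 × (1 − 0.741) = 20.0.
- P(stop | 60%) = P(X ≤ 5 | 12, 0.60) = 0.158, so power cannot exceed 0.842. With the best final cut-off that keeps alpha at or below 0.05 (at least 21 of 43, alpha 0.0499), power is 0.819.
- The stated beta of 0.10 is therefore not reproduced. An exact search for 0.37/0.60/0.05/0.10 gives n1 = 20 (go at 9 or more) and N = 44. With beta 0.20 the optimum is n1 = 12 (go at 6 or more) and N = 38.

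**2. Enrolled when all 12 outcomes are known, no pause.** Patient 12 enters at 12/rate, and enrolled at the read = 12 + 6 × rate.

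| Window | Rate per month | Patient 12 enters | Gate complete | Enrolled | Of 31 in stage 2 |
|---|---|---|---|---|---|
| 12 months | 43/12 = 3.58 | month 3.3 | month 9.3 | 33.5 | 21.5 (69%) |
| 13 months | 43/13 = 3.31 | month 3.6 | month 9.6 | 31.8 | 19.8 (64%) |

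Sensitivities:
- Reading at the week-24 scan (5.52 months) gives 18 to 20 of 31.
- Allowing one extra month for central review (an assumption) gives 23 to 25 of 31.
- Accrual curves 43(t/T)^k with k from 0.5 to 3 give 31.6 to 43 enrolled.
- Half or less of stage 2 would be enrolled only at 15.5/6 = 2.58 per month or slower, that is, 43 patients in at least 16.6 months.

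**3. Stop called at the 7th failure.** Simulation with exponential PFS (37% at 6 months), 8-weekly scans, uniform accrual and no hold: a stop comes at a median of about month 7 with a mean of 23.4 to 24.7 enrolled. That is 11.4 to 12.7 of 31 (37 to 41%). More than half of stage 2 is enrolled in 17 to 27% of stops.

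**4. Consequence at the null.**
- Patients spared by a stop: 31 as designed; 43 − 33.5 = 9.5 to 43 − 31.8 = 11.2 at the full read; 43 − 24.7 = 18.3 to 43 − 23.4 = 19.6 at the 7th failure.
- Expected sample size: 20.0 as designed; 0.741 × 31.8 + 0.259 × 43 = 34.7 to 0.741 × 33.5 + 0.259 × 43 = 36.0 at the full read; 0.741 × 23.4 + 0.259 × 43 = 28.5 to 0.741 × 24.7 + 0.259 × 43 = 29.4 at the 7th failure.

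**5. Does a full hold fit the calendar?** Inside the stated window it needs 43/(12 − 6) = 7.2 or 43/(13 − 6) = 6.1 per month. At the no-pause rates, accrual lasts 12 + 6 = 18 or 13 + 6 = 19 months. The last patient then enters about July to August 2019, after the stated June 2019 end of study, and reaches 6 months at month 24 to 25.

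**The case against.** **Stage 2 is worded as conditional.** Read plainly, the 31 patients come after the six successes, and no sentence says that accrual runs through the gate. This stands: the absence of a hold is inferred from silence. But the calendar accommodates the conditional reading only at about 6 to 7 patients per month, and nothing in the protocol supports or excludes that rate.

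**The accrual rate is partly circular.** The dates are estimates, and 3.3 to 3.6 per month presumes no pause. Correct, which is why the result is given for that reading alone, beside the rate that a pause would require.

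**A stop need not wait for all 12.** This also stands. A reader might infer that most of stage 2 would be enrolled before any stop. With a decision at the 7th failure the average is 37 to 41% of stage 2, so *most* applies to the full 12-patient read only.

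**The DMC can act on efficacy data.** Section 10.5 lets it recommend termination and leaves its operation to a charter, and Section 4.5 allows efficacy data to end the study. That is general authority. It does not schedule a review of the gate.

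**Enrolment may seem already to have passed the gate.** The study table in Section 1.2.2.3.2 lists a one-arm trial of this combination in "progressive osteosarcoma with chemotherapy failure | One-arm, open-label, phase II study | 2017-12/37 | NCT03359018" ("Cut-off date: 25 Aug 2018"). If that is this trial, its rate (37 patients in roughly 7.8 to 8.8 months) would put about 37 to 40 enrolled at the full read. Identity is not established: the row is described as multicenter while this trial is single-center, its first case precedes the estimated start, and its registration number is repeated for a lung cancer study. It is supporting evidence at most, and the protocol does not show that the trial departed from its design.

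**Conclusion.** The point holds in this form: the protocol makes stage 2 depend on a 6-month outcome but gives neither a hold nor a scheduled review, and its calendar, followed at the rate it implies without a pause, largely overruns the gate. When all 12 outcomes are known, 32 to 34 of 43 patients are enrolled (20 to 22 of 31 in stage 2). With a stop at the 7th failure, about 23 to 25 are enrolled (11 to 13 of 31). These figures rest on uniform accrual over estimated dates, and the second pair also on exponential PFS with 8-weekly scans.

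A reader might infer that the overrun inflates the false-positive rate. It does not, provided the gate remains binding. What is lost is early-stopping protection and the expected sample size of 20.0 at the null.

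**What to change.** 1. Settle the stage-1 size first. The 12-patient gate alone stops a 60% regimen 15.8% of the time, so it cannot meet the stated beta of 0.10. A hold should not be written around it until design and error rates agree. If stage 1 became 20 patients, the overrun without a hold would be larger: 20 + 6 × 3.58 = 41.5 enrolled at the full read on the 12-month window.
2. In Sections 10.1 and 10.4.5 (and the Synopsis), state that enrolment is held after the last stage-1 patient until the gate is settled. If the gate stays at 6 of 12, settle it at the 7th failure (stop) or the 6th confirmed 6-month success (go). This is the same rule as at least 6 of 12, so its operating characteristics do not change.
3. Add this review to Section 10.5.
4. Revise both the last-enrolment and end-of-study dates in the Synopsis and Section 16, and reconcile them with the 18 months in Section 4.6. Moving only the enrolment date would put last enrolment after the stated end of study.
5. If enrolment has already passed the gate, report how many stage-2 patients entered before the result was known.

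The hold costs an accrual pause of up to about 6 months, shortened by the early-decision rule, plus the wording and later dates. It needs no extra patients or procedures. Changing the stage-1 size in step 1 may alter the total.
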